6.4.2 Follow-up of unresolved adverse events

Any AEs that are unresolved at the subject's last AE assessment or other assessment/visit as appropriate in the study are followed up by the Investigator for medical needs, but without further recording in the CRF. AstraZeneca retains the right to request additional information for any subject with ongoing AE(s)/SAE(s) at the end of the study, if judged necessary.

6.4.3 Variables

The following variables will be collect for each AE:

- AE (verbatim)
- The date and time (if applicable) when the AE started and stopped
- max CTCAE grade
- Whether the AE is serious or not
- Investigator causality rating against the IP (yes or no)
- Action taken with regard to IP
- Outcome.

In addition, the following variables will be collected for SAEs:

- Date AE met criteria for serious AE
- Date Investigator became aware of serious AE
- AE is serious due to
- Date of hospitalization (if applicable)
- Date of discharge (if applicable)
- Probable cause of death (if applicable)
- Date of death (if applicable)
- Autopsy performed (yes or no; if yes provide report) (if applicable)
- Causality assessment in relation to Study procedure(s)
- Description of AE.

It is important to distinguish between serious and severe AEs. Severity is a measure of intensity whereas seriousness is defined by the criteria in Section 6.2. An AE of severe intensity need not necessarily be considered serious. For example, nausea that persists for several hours may be considered severe nausea, but not a SAE unless it meets the criteria shown in Section 6.2. On the other hand, a stroke that results in only a limited degree of disability may be considered a mild stroke but would be a SAE when it satisfies the criteria shown in Section 6.2.

6.4.4 Causality collection

The Investigator will assess causal relationship between IP and each Adverse Event, and answer 'yes' or 'no' to the question 'Do you consider that there is a reasonable possibility that the event may have been caused by the IP?'

For SAEs causal relationship will also be assessed for other medication and study procedures. Note that for SAEs that could be associated with any study procedure the causal relationship is implied as 'yes'.

A guide to the interpretation of the causality question is found in Appendix A to the Clinical Study Protocol.

6.4.5 Adverse events based on signs and symptoms

All AEs spontaneously reported by the subject or reported in response to the open question from the study personnel: '*Have you had any health problems since the previous visit/you were last asked?*', or revealed by observation will be collected and recorded appropriately according to the AE collection time period (section 6.4.1). When collecting AEs, the recording of diagnoses is preferred (when possible) to recording a list of signs and symptoms. However, if a diagnosis is known and there are other signs or symptoms that are not generally part of the diagnosis, the diagnosis and each sign or symptom will be recorded separately.

6.4.6 Adverse events based on examinations and tests

The results from protocol mandated laboratory tests and vital signs will be summarised in the CSR. Deterioration as compared to baseline in protocol-mandated laboratory values, vital signs and ECG abnormalities should therefore only be reported as AEs if they fulfil any of the SAE criteria or are the reason for discontinuation/interruption/dose reduction of treatment with the IP, or if the investigator believes that the abnormality should be reported as an AE.

If deterioration in a laboratory value/vital sign is associated with clinical signs and symptoms, the sign or symptom will be reported as an AE and the associated laboratory result/vital sign will be considered as additional information. Wherever possible the reporting Investigator uses the clinical, rather than the laboratory term (e.g., anaemia versus low haemoglobin value). In

the absence of clinical signs or symptoms, clinically relevant deteriorations in non-mandated parameters should be reported as AE(s).

Deterioration of a laboratory value, which is unequivocally due to disease progression, should not be reported as an AE/SAE.

Any new or aggravated clinically relevant abnormal medical finding at a physical examination as compared with the baseline assessment will be reported as an AE.

6.4.7 Disease progression

Disease progression can be considered as a worsening of a subject's condition attributable to the disease for which the IP is being studied. It may be an increase in the severity of the disease under study and/or increases in the symptoms of the disease. The development of new, or progression of existing metastasis to the primary cancer under study should be considered as disease progression and not an AE. Events, which are unequivocally due to disease progression, should not be reported as an AE during the study.

6.4.8 New cancers

The development of a new cancer should be regarded as an SAE. New primary cancers are those that are not the primary reason for the administration of the IP and have been identified after the patient's inclusion in this study.

6.4.9 Deaths

All deaths that occur during the study must be reported as follows:

• Death clearly the result of disease progression should be reported to the study monitor at the next monitoring visit and should be documented in the eCRF but should not be reported as an SAE.

• Where death is not due (or not clearly due) to progression of the disease under study, the AE causing the death must be reported to the study monitor as a SAE within 24 hours. The report should contain a comment regarding the co involvement of progression of disease, if appropriate, and should assign main and contributory causes of death.

• Deaths with an unknown cause should always be reported as a SAE. A post mortem maybe helpful in the assessment of the cause of death, and if performed a copy of the post-mortem results should be forwarded to AstraZeneca within the usual timeframes .

6.5 **Reporting of serious adverse events**

All SAEs from the time of informed consent up to 12weeks after the last dose of Zoladex have to be reported, whether or not considered causally related to the IP, or to the study procedure(s). All SAEs will be recorded in the CRF.

If any SAE occurs in the course of the study, then Investigators or other site personnel inform the appropriate AstraZeneca representatives within one day i.e., immediately but **no later than 24 hours** of when he or she becomes aware of it.

The designated AstraZeneca representative works with the Investigator to ensure that all the necessary information is provided to the AstraZeneca Patient Safety data entry site within 1 calendar day of initial receipt for fatal and life threatening events and within 5 calendar days of initial receipt for all other SAEs. In addition, the investigator should report the SAE to China Authority according to local regulation and Local Ethics Committee (EC) according to local requirement.

For fatal or life-threatening AEs where important or relevant information is missing, active follow-up is undertaken immediately. Investigators or other site personnel inform AstraZeneca representatives of any follow-up information on a previously reported SAE within one calendar day i.e., immediately but **no later than 24 hours** of when he or she becomes aware of it.

Once the Investigators or other site personnel indicate an AE is serious in the EDC system, an automated email alert is sent to the designated AstraZeneca representative.

If the EDC system is not available, then the Investigator or other study site personnel reports a SAE to the appropriate AstraZeneca representative by telephone.

The AstraZeneca representative will advise the Investigator/study site personnel how to proceed.

Investigators or other site personnel send relevant information by fax to the designated AstraZeneca representative.

6.6 Reporting non-serious of adverse drug reactions

All ADRs (i.e., Adverse Events suspected to be causally related to AstraZeneca Investigational Product) from the time of informed consent until 12weeks after the last dose of Zoladex should be reported to AstraZeneca.

If any non-serious ADR occurs in the course of the study, the investigator should inform the appropriate AstraZeneca representatives **within 5 calendar days** of when he or she becomes aware of it.

The designated AstraZeneca representatives should work with the investigator to ensure all necessary information is provided to AstraZeneca Patients Safety Data Entry Site within 5 calendar days of initial receipt.

Contact information of AZ Data Entry Site:

The below e-mail address should be used for the RAVE automatic SAE e-mail notifications:

[contact]

The following e-mail address should be used for all other clinical study case reports: [contact]

[contact], back up [contact]

6.7 Overdose

For this study, any dose of Zoladex greater than 10.8mg per 12 weeks and/or Casodex 50mg per day will be considered an overdose. Adverse events associated with overdose should be treated symptomatically and should be managed appropriately.

For Zoladex:

The pharmacologic properties of Zoladex and its mode of administration make accidental or intentional overdose unlikely. There is no experience of overdose from clinical trials. Animal studies indicate that no increased pharmacologic effect occurred at higher doses or more frequent administration. Subcutaneous doses of the drug as high as 1 mg/kg/day in rats and dogs did not produce any nonendocrine related sequelae; this dose is up to 250 times the estimated human daily dose based on the body surface area. If overdose occurs, it should be managed symptomatically.

For Casodex:

Long-term clinical trials have been conducted with dosages up to 200 mg of Casodex daily and these dosages have been well tolerated. A single dose of Casodex that results in symptoms of an overdose considered to be life threatening has not been established.

There is no specific antidote; treatment of an overdose should be symptomatic.

In the management of an overdose with Casodex, vomiting may be induced if the subject is alert. It should be remembered that, in this patient population, multiple drugs may have been taken. Dialysis is not likely to be helpful since Casodex is highly protein bound and is extensively metabolized. General supportive care, including frequent monitoring of vital signs and close observation of the subject, is indicated.

If an overdose occurs, the rules follows in below:

- An overdose with associated AEs is recorded as the AE diagnosis/symptoms on the relevant AE modules and on the Overdose CRF module.
- An overdose without associated symptoms is only reported on the Overdose CRF module.

If an overdose on an AstraZeneca study drug occurs in the course of the study, then the Investigator or other site personnel inform appropriate AstraZeneca representatives immediately, or **no later than 24 hours** of when he or she becomes aware of it.

The designated AstraZeneca representative works with the Investigator to ensure that all relevant information is completed within **1 or 5 calendar days** if there is an SAE associated with the overdose (See section 6.4), within **5 calendar days** for non-serious ADR (see Section 6.6) and within 30 days for all other overdose.

6.8 Pregnancy

All pregnancies and outcomes of pregnancy should be reported to AstraZeneca except for:.

If the pregnancy is discovered before the study subject has received any study drug.

If a pregnancy is reported, the investigator should inform the sponsor within **24 hours** of learning of the pregnancy. Abnormal pregnancy outcomes (eg, spontaneous abortion, foetal death, stillbirth, congenital anomalies, ectopic pregnancy) are considered SAEs.

6.8.1 Paternal exposure

Male subjects must be surgically sterile or using an acceptable method of contraception (defined as barrier methods in conjunction with spermicides) for the duration of the study (from the time they sign consent) and for 3 months after the last dose of Study Drugs to prevent pregnancy in a partner.

Pregnancy of the subject's partners is not considered to be an adverse event. However, the outcome of all pregnancies (spontaneous miscarriage, elective termination, ectopic pregnancy, normal birth or congenital abnormality) should if possible be followed up and documented.

Where a report of pregnancy is received, prior to obtaining information about the pregnancy, the Investigator must obtain the consent of the patient's partner.

6.9 Medication error

For the purposes of this clinical study a medication error is an unintended failure or mistake in the treatment process for an AstraZeneca study drug that either causes harm to the subject or has the potential to cause harm to the subject.

A medication error is not lack of efficacy of the drug, but rather a human or process related failure while the drug is in control of the study centre staff or subject.

Medication error includes situations where an error

- Occurred
- Was identified and intercepted before the subject received the drug
- Did not occur, but circumstances were recognise that could have led to an error.

Examples of events to be reported in clinical studies as medication errors:

- Drug name confusion
- Dispensing error e.g., medication prepared incorrectly, even if it was not actually given to the subject
- Drug not administered as indicated, for example, wrong route or wrong site of administration
- Drug not taken as indicated e.g., tablet dissolved in water when it should be taken as a solid tablet
- Drug not stored as instructed e.g., kept in the fridge when it should be at room temperature
- Wrong subject received the medication (excluding IVRS/IWRS errors)
- Wrong drug administered to subject (excluding IVRS/IWRS errors).

Examples of events that do not require reporting as medication errors in clinical studies:

• Errors related to or resulting from IVRS/IWRS - including those which lead to one of the above listed events that would otherwise have been a medication error

- Subject accidentally missed drug dose(s) e.g., forgot to take medication
- Accidental overdose (will be captured as an overdose)
- Subject failed to return unused medication or empty packaging
- Errors related to background and rescue medication, or standard of care medication in open label studies, even if an AZ product

Medication errors are not regarded as AEs but AEs may occur as a consequence of the medication error.

If a medication error occurs in the course of the study, then the Investigator or other site personnel informs the appropriate AstraZeneca representatives within 1 day, i.e., immediately but no later than 24 hours of when he or she becomes aware of it.

The designated AstraZeneca representative works with the Investigator to ensure that all relevant information is completed within 1 or 5 calendar days if there is an SAE associated with the medication error (See section 6.4), within 5 calendar days for non-serious ADR (see Section 6.6) and within 30 days for all other medication errors.

6.10 Management of IP related toxicities

Laboratory abnormalities including elevated AST, ALT, bilirubin, BUN (blood urea nitrogen), and creatinine and decreased hemoglobin and white cell count have been reported in both Casodex-LHRH analogue treated and flutamide-LHRH analogue treated subjects.

Rare cases of death or hospitalization due to severe liver injury have been reported postmarketing in association with the use of Casodex. Hepatotoxicity in these reports generally occurred within the first three to four months of treatment. Hepatitis or marked increases in liver enzymes leading to drug discontinuation occurred in approximately 1% of Casodex patients in controlled clinical trials.

Serum transaminase levels should be measured prior to starting treatment with Casodex, at regular intervals for the first four months of treatment, and periodically thereafter. If clinical symptoms or signs suggestive of liver dysfunction occur (e.g., nausea, vomiting, abdominal pain, fatigue, anorexia, "flu-like" symptoms, dark urine, jaundice, or right upper quadrant tenderness), the serum transaminases, in particular the serum ALT, should be measured immediately. If at any time a subject has jaundice, or their ALT rises above two times the upper limit of normal, Casodex should be immediately discontinued with close follow-up of liver function.

7 INVESTIGATIONAL PRODUCT AND OTHER TREATMENTS

7.1 Identity of investigational pro	oduct(s)
-------------------------------------	----------

Investigational product	Dosage form and strength	Manufacturer
Zoladex [®] (goserelin acetate implant)	Implant 10.8 mg	AstraZeneca
Casodex [®] (bicalutamide)	Film-coated Tablets 50 mg	AstraZeneca

Zoladex[®] 10.8 mg implant is supplied as sterile and totally biodegradable D. L-lactic and glycolic acids copolymer (12.8-14.76 mg/dose) impregnated with goserelin acetate equivalent to 10.8 mg goserelin in a disposable Syringe device fitted with a 14-gauges x 36 +/- 0.5 mm siliconized hypodermic needle with protective sleeve [SafeSystemTM Syringe]. The Unit is sterile and comes in a sealed, light- and moisture-proof, aluminum foil laminate pouch containing a desiccant capsule. Store at room temperature (do not exceed 25°C).

For Casodex[®] (bicalutamide) of 50 mg Tablets white, film-coated tablets (identified on one side with "CDX50" and on the reverse with the "Casodex logo") are supplied in unit dose blisters of 98 tablets per carton. The Store temperature is less than 30°C.

7.2 Dose and treatment regimens

Zoladex[®] 10.8 mg implant will be administered subcutaneously every 12 weeks for 24 weeks.

Casodex[®] in combination with Zoladex[®] is one 50 mg tablet once daily (morning or evening), with or without food. It is recommended that Casodex[®] be taken at the same time each day. Treatment with Casodex[®] should be started at the same time as treatment with Zoladex[®] and continued for 24 weeks.

Treatment after RP will be dependent on the investigator's discretion.

7.3 Labelling

Labels will be prepared in accordance with Good Manufacturing Practice (GMP) and local regulatory guidelines. The labels will fulfil GMP Annex 13 requirements for labelling. Label text will be translated into local language.

The label will include the following information:

- Name of sponsor (AstraZeneca)
- Investigational product/study drug dosage form, route of administration, and quantity of dosage units

- Storage conditions
- Study code
- Enrolment code
- Directions for use
- The period of use e.g., expiry date
- For clinical study use only
- Keep out of reach of children

7.4 Storage

All study drugs should be kept in a secure place under appropriate storage conditions. The IP label on the pack/bottle specifies the appropriate storage.

Zoladex[®] 10.8 mg implant is required to store at room temperature (do not exceed 25°C) and Casodex[®] (bicalutamide) of 50 mg tablets is required to store at less than 30°C temperature.

7.5 Compliance

The administration of all study drugs (including investigational products) should be recorded.

7.6 Accountability

The IP provided for this study will be used only as directed in the study protocol.

The study personnel will account for all IP dispensed to and returned from the subject.

Study site personnel or the study monitor will account for IP received at the site, unused study drugs and for appropriate destruction. Certificates of delivery, destruction or return should be signed.

7.7 Concomitant and other treatments

Prohibited Medication/Class of Drug:	Usage:
Other LHRH agonists include, not limited to: triptorelin / leuprorelin	Not permitted to be used before RP
Other antiandrogens include, not limited to: flutamide / nilutamide	Not permitted to be used before RP

7.7.1 Other concomitant treatment

Other medication other than that described above, which is considered necessary for the subject's safety and well-being, may be given at the discretion of the Investigator and recorded.

7.8 Post study access to study treatment

If ADT after RP will be given to subjects based on investigator's discretion, either Zoladex [®] 10.8 mg implant or Casodex[®] (bicalutamide) of 50 mg Tablets will not be provided by Astrazeneca. Zoladex[®] 10.8 mg implant and Casodex[®] (bicalutamide) of 50 mg Tablets have been available on market. It will be easy to access the medication by the subjects.

8 STATISTICAL ANALYSES BY ASTRAZENECA

8.1 Statistical considerations

A comprehensive Statistical Analysis Plan (SAP) will be prepared prior to first subject enrolled and any subsequent amendments will be documented, with final amendments completed prior to lock of the data for the primary analysis. Analyses will be performed by AstraZeneca or its representatives.

8.2 Sample size estimate

This is a single-arm, prospective study and the primary endpoint is the actual radical prostatectomy rate. An approximate sample size of 104 subjects provides a precision of 6.1% based on the bilateral 95% confidence interval (CI) for the resectability rate of 90% assuming a dropout rate of 10% (half width of 95% CI).

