8.3 Definitions of analysis sets

Full analysis set (FAS)

The FAS will include all subjects who received at least one dose of study treatment, irrespective of whether some of these subjects may have discontinued treatment prior to the trial's end.

RP analysis set (**RPAS**)

The RPAS is defined as a subset of FAS, which includes all FAS subjects who actually received RP within 30 days by the end of NHT, regardless of prematurely discontinued treatment.

All RP related assessments will be conducted based on RPAS except for the primary analysis, where the denominator will be number of subjects in FAS.

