8.4 Outcome measures for analyses

8.4.1 Primary endpoint

Actual radical prostatectomy rate

Actual radical prostatectomy rate is defined as the rate of the subjects who perform radical prostatectomy within 30 days after end of NHT

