8.5 Methods for statistical analyses

8.5.1 Descriptive analyses will be utilized for all endpoints. Continuous variables will be summarised by the number of observations (n), mean (or geometric mean if appropriate), standard deviation (SD), median, quartiles (Q1 and Q3), minimum, and maximum. Categorical variables will be summarised by frequency counts and percentages for each category. The 95% CI will be provided when appropriate. Analysis of the primary variable (s)

The number of subjects to receive radical prostatectomy after NHT will be summarised. The resectability rate will be calculated with 95% CI provided using the Clopper-Pearson method.

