1.3 Number of subjects

This is a single-arm, prospective study and the primary endpoint is the actual radical prostatectomy rate. An approximate sample size of 104 subjects provides a precision of 6.1% based on the bilateral 95% confidence interval (CI) for the resectability rate of 90% assuming a dropout rate of 10% (half width of 95% CI).

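### The stated 6.1% precision fits a Wald interval on 93 subjects with drop-outs removed, but the primary analysis is Clopper-Pearson on all treated subjects, where the half-width is about 6.2% to 7.9% depending on what the 90% means.

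*Protocol*

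**What the plan says.** Precision is the only justification given for the sample size. Protocol 8.2 states: "An approximate sample size of 104 subjects provides a precision of 6.1% based on the bilateral 95% confidence interval (CI) for the resectability rate". SAP 1.3 repeats the sentence and completes it with the assumptions: "for the resectability rate of 90% assuming a dropout rate of 10% (half width of 95% CI". The synopsis has the same text. None of the three places names the interval method or says how drop-out enters the calculation.

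The analysis is defined elsewhere:

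- **Interval.** Protocol 8.5.1: "The resectability rate will be calculated with 95% CI provided using the Clopper-Pearson method". SAP 4.3.6 gives a 95% interval without naming a method.
- **Denominator.** Protocol 8.3 bases surgery-related assessments on the operated subset, "except for the primary analysis, where the denominator will be number of subjects in FAS". Of the FAS it says: "The FAS will include all subjects who received at least one dose of study treatment". SAP 2.1 and 3.1 use the same denominator.
- **Event.** Protocol 8.4.1 defines the endpoint as "the rate of the subjects who perform radical prostatectomy within 30 days after end of NHT". SAP 3.1 counts subjects who stopped treatment early but were operated.
- **Losses.** Protocol 3.7.2 does not replace withdrawn subjects, and SAP 4.2 does not impute missing outcomes.

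**The concern.** The planning sentence and the analysis appear to treat a drop-out in opposite ways. Allowing for drop-out by inflating the sample size assumes that lost subjects leave the denominator and that the rate applies to those who remain. The FAS keeps every treated subject, so one who is lost without radical prostatectomy (RP) counts as not operated. Such losses leave the denominator at 104 and lower the rate. A proportion further from 100% has a wider interval. Clopper-Pearson is also wider than the normal approximation at the same sample size and rate.

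The study has no hypothesis test or success threshold, so no error rate is affected. What is at stake is whether the stated precision, the sole basis for 104 subjects, describes the interval that will be reported, and whether a reader can tell which rate the 90% refers to.

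**Working it through.** **Inputs.** N = 104, half-width 6.1%, two-sided 95%, rate 90%, drop-out 10% (Protocol 8.2, SAP 1.3). Clopper-Pearson (Protocol 8.5.1). FAS denominator (Protocol 8.3, SAP 2.1 and 3.1).

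**1. Reproducing the plan's figure.** The Wald half-width is 1.96 × √(p(1−p)/n).

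- Solving for 6.1% at p = 0.90: n = 1.96² × 0.09 / 0.061² = 92.9, so 93.
- Check: 1.96 × √(0.09/93) = 6.10%.
- Drop-out: 93/0.9 = 103.3, rounded up to 104.

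This gives both 6.1% and 104 and uses the stated drop-out. Other methods at 90%:

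| Method | n = 93 | n = 104 |
|---|---|---|
| Wald | 6.10% | 5.77% |
| Wilson | 6.18% | 5.84% |
| Clopper-Pearson | 6.5% (84 operated) to 6.8% (83) | 6.13% (94 operated) to 6.37% (93) |

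Clopper-Pearson on 94/104 also rounds to 6.1%, but it makes no use of the 10% drop-out.

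**2. The planned analysis.** With x operated out of n, the Clopper-Pearson limits are the 2.5% quantile of Beta(x, n−x+1) and the 97.5% quantile of Beta(x+1, n−x). The expected half-width averages half of (upper − lower) over Binomial(n, p). The documents do not say when drop-outs leave or whether they are operated, so four readings are shown.

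| Reading of the 10% and the 90% | FAS | Expected RP rate | Expected half-width |
|---|---|---|---|
| All drop-outs treated, none operated; 90% of the rest operated | 104 | 0.9 × 0.9 = 81% | 7.89% |
| As above, but half of the drop-outs operated at the 90% rate | 104 | 0.9 × (0.9 + 0.05) = 85.5% | 7.13% |
| All drop-outs leave before the first dose | about 93 | 90% | 6.52% |
| 90% is already the rate over all treated | 104 | 90% | 6.15% |

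Examples for the first reading: 84/104 = 80.8%, interval 71.9% to 87.8%, half-width 7.98%; 85/104 = 81.7%, interval 73.0% to 88.6%, half-width 7.84%. For the third: 84/93 = 90.3%, interval 82.4% to 95.5%, half-width 6.53%. In the fourth, the half-width at exactly 90% is 6.23%, so about 6.2% either way.

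**3. Where the gap comes from.** In the first reading, Wald on 104 at 81% is already 1.96 × √(0.81 × 0.19/104) = 7.54%. The denominator and the lower rate therefore account for 7.54 − 6.10 = 1.44 points, and Clopper-Pearson adds 7.89 − 7.54 = 0.35.

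**The case against.** The strongest reply is that 7.9% is not the plan's own figure. It needs every drop-out to occur after the first dose, none of them to be operated, and the 90% to apply only to the remainder. The documents state none of these. Subjects lost before dosing never enter the FAS, and those who stop treatment early but are operated count as events. That stands, so 7.9% is the upper case among the readings considered.

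It can also be said that 6.1% does not prove a Wald calculation on 93, because 94/104 by Clopper-Pearson gives 6.13%. That stands too. Wald on 93 is an inference, though the only derivation found that uses the stated drop-out and returns both figures. The alternative leaves the 10% with nothing to do, so the sentence would still need correcting.

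The consequence is also limited. The study is descriptive, the sample size is called approximate, and the reported interval will come from the observed data whatever Protocol 8.2 says. This limits the importance of the point but does not make the sentence describe the planned analysis.

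A reader might infer from the term resectability rate that a second primary quantity is in play. The documents do not support this. Protocol 8.2 names the actual RP rate as the endpoint in the preceding sentence, and Protocol 8.4.1, SAP 3.1 and SAP 4.3.6 all count operated subjects. The wording is loose, but the quantity to be computed is clear.

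**Conclusion.** The precision sentence is wrong as written for the planned analysis. Its figure matches a calculation that removes drop-outs, whereas the analysis keeps treated drop-outs in the denominator and uses a wider interval. Under the four readings the expected half-width is about 6.2%, 6.5%, 7.1% or 7.9%. The first of these comes close to the stated 6.1%, but only by leaving the drop-out assumption without a role. At the upper case the interval is about 30% wider than stated (7.89/6.10 = 1.29).

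Two stronger conclusions are tempting. One is that the true precision is 7.9%. The documents do not fix the timing or surgical outcome of drop-outs, so that figure is conditional on all drop-outs being treated and none operated. The other is that an observed rate near 81% would be a shortfall against 90%. The documents give 90% as a planning value and set no target, and in the first reading 81% is what the assumptions predict. The primary estimate and its reported interval remain valid.

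**What to change.** Keep 104. In the synopsis, Protocol 8.2 and SAP 1.3, state whether the 90% already counts drop-outs as not operated, and restate the precision by Clopper-Pearson on the FAS:

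- If it does not: with 104 treated, 10% lost without surgery and 90% of the rest operated, the expected rate is 81% and the half-width about 7.9%.
- If it does: the rate over all 104 treated is 90% and the half-width about 6.2%, and the drop-out allowance is deleted from the sentence.

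Replace resectability rate by actual radical prostatectomy rate in the synopsis, Protocol 8.2 and 8.5.1, and SAP 1.3.

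The cost is wording only, with no change to enrolment, conduct or data collection. The downside is that the stated precision becomes less favourable.
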